7.4.6 Receiving, Storage, Dispensing and Return

7.4.6.1 Receipt of Test Article

The SREC device will be purchased from NJOY, LLC in its standard packaging and shipped to Penn State and will be received by unblinded staff. Pre-filled, sealed, disposable pods containing 1.9 mL of e-cig liquid will also be purchased from NJOY. The pods will come in blister packs containing 2 pods.

7.4.6.2 Storage

All study products (e.g., SREC devices, pods) and components will be stored in TCORS space in a locked closet in Room H7514 away from light, heat, and moisture.

7.4.6.3 Preparation and Dispensing

The pods will come pre-filled in individually sealed packages. They will be prepared for participants by unblinded staff and stored with unique identifiers. Unblinded staff will appropriately package kits containing two SREC devices and a supply of filled pods for the participants. At Visit 1, following confirmation of eligibility for randomization, participants will be randomly assigned a kit number. The blinded researchers will not be involved in the packing and labeling of the kits.

All receiving, sorting, blinding, and dispensing of the study product will be done in the TCORS pharmacy space at Penn State in Room H7514.

7.4.6.4 Return or Destruction of the Test Article

Participants will be dispose of their SREC device and all used and unused pods after completion of Phone Contact #5or if they are withdrawn. The devices provided to participants in this study are not commercially available and thus cannot be used without the pods provided in the study.

7.4.6.5 Prior and Concomitant Therapy

Concomitant medication use will be collected regularly throughout the trial and to monitor participant health conditions.

Participants taking varenicline, bupropion or nortriptyline as a smoking cessation medication in the prior month will be excluded from the study. Participants taking bupropion or nortriptyline for depression management and who expect to continue use of the medication throughout the trial will be eligible to participate. Additionally, participants who are prescribed bupropion or nortriptyline for depression management at any point during the study will be eligible to continue with the study. Medications related to certain medical conditions that are exclusions to the study, such as COPD and current heart conditions, will serve to alert the study staff of the presence of these conditions during screening. Once the participant is entered into the randomized double blind phase of the study, there are no medications that will interfere with the participant's ability to participate.

8.0 Subject Numbers and Statistical Plan

8.1 Number of Subjects

Participants will be enrolled in the study until a total of 240 are randomized. We anticipate that we will need to enroll up to 300 participants in order to randomize 240.

8.2 Sample size determination

We plan to randomize a total of 240 participants (120 in each dose group), and it is assumed that, although all efforts will be made to ensure 100% retention in the trial, as many as 30% of participants may drop-out after randomization. Thus, the effective sample size for this study could be as low as 84 per group, as the primary study endpoint is measured and collected at the last in-person study Visit 4.

Therefore, n=84 is the expected number of participants in each group to complete Visit 4 (e.g. complete the 'Switching Phase' of the study). It is expected that the NNAL levels in the nicotine-containing e-cigs group will be similar to results obtained by Goniewicz et al¹³ assuming a pre-treatment mean =225ng/ml creatinine (SD 165) vs. post-treatment 80 ng/ml creatinine (SD=69). The pre-treatment values of the placebo e-cigs group are expected to be similar to that of the nicotine-containing e-cigs group, as this measure occurs prior to randomization. The n=84 per group sample size should enable us to detect a post-treatment NNAL difference of 35 ng/ml creatinine or larger between groups (i.e., the placebo e-cigs group's post-treatment NNAL mean value be > 115), with at least 90% statistical power under 5% type 1 error.

8.3 Statistical methods

For the analysis, the baseline time will be Visit 1, prior to randomization to an e-cig nicotine content regimen (placebo or nicotine), which occurs at end of Visit 1.

Summary statistics will be provided for baseline smoking characteristics, along with other study demographics collected upon enrollment/screening at Visit 1. Summary statistics will also be provided for all variables at each visit. This will include all randomized subjects.

Aim 1: For each battery of measures, the mean change from week 1 to week 6 will be estimated with a corresponding 95% confidence interval. The p-value for testing zero underlying change will also be provided. This analysis will be conducted separately for the two treatment arms. To adjust for multiple comparisons, the false discovery approach will be used. Additionally, the trajectory of each measurement at visit 1 visit 2 and visit 3 will be modeled using linear mixed effects regression.

Aim 2: The difference between the two treatment arms on markers of health risk will be analyzed. The primary conceptual framework is a modified intent-to-treat: subjects will be analyzed by their randomized arm regardless of compliance with the e-cig nicotine content regimen, as long as data for the particular outcome is available at either of the post-randomization visits (Visit 2 or Visit 3). The basic statistical tool will be linear regression or logistic regression. Two sets of regressions will be conducted. The first set of regressions will model the dependence of the outcome measures at week 6 on the two treatment arms while controlling for the baseline value of the outcome variable. The second set of regressions will adjust for additional covariates at baseline (V1), to be selected via backward elimination at 0.05 significance level. These additional covariates will be chosen from the following list based on appropriateness for the specific outcome variable.

- Age
- Race
- Hispanic
- Education status
- Gender
- Income
- SDOH questionnaire (ACES score)
- Baseline cpd
- Baseline CO
- Baseline NNAL
- Baseline cotinine
- Menthol/non-menthol cigarettes
- Cigarette length
- Height
- Weight
- BMI

- Baseline FEV1
- Baseline PSCDI
- Quit attempt history
- "Currently, do you have any symptoms or a disease that you believe is caused or made worse by your tobacco use?" (yes/no)
- Perceived cessation support questions
- ETS questionnaire
- Baseline MNWS
- Baseline QSU
- Baseline audit c
- Baseline cigarette perceived health rick score
- E-cig Perceived risk/Perceptions of e-cig risks (from screener)
- Baseline CESD
- Baseline Kessler 6
- Baseline perceived stress
- Baseline COPD questionnaire
- Baseline interheart
- Importance and confidence to quit

Same strategy will be used for withdrawal items on the MNWS and scores on ratings of cigarette craving. The analysis will be conducted for the values of these variables at week 3, however.

Cigarette Abstainers Subgroup Analysis

In addition to the intent-to-treat analysis, additional analysis on subgroup of regular cigarette abstainers only will be conducted. By design, this subgroup will only consist of Switching Phase Completers (still in the study at the time of V3) who have successfully abstained from cigarette and other tobacco use (except e-cigs) from 1 week prior to V2 consistently and consecutively until V3. Therefore, this subgroup would be defined as 'quit' for at least 4 weeks. Participants in this sub-group must also have an exhaled CO < 6 ppm at both V2 and V3. Based on our previous data, we believe that 40% of the nicotine e-cig group (84 x .40 = roughly 33 participants) and 20% of the placebo e-cig group (84 x .20 = roughly 16 participants) will be classified as abstainers. For this relatively small subgroup, we shall only model the dependence of the outcome measures at week 6 on the two treatment arms while controlling for the baseline value of the outcome variable. No elaborate adjustment of other covariates will be included.

Aim 3: The proportions of subjects who will try to abstain from cigarettes and who will continue to use an e-cig at week 10 will be compared between the two arms using Fisher's exact test. Switching Phase dropouts will be treated as 'non-abstainers' from cigarettes under the 'worst case-scenario' assumption. A supplementary logistic regression will also be conducted to explore their dependence on demographic variables in addition to the two treatment arms.

Multiple imputation for missing values

We will strive to minimize the number of missing values by rigorous follow-up with the study subjects. In spite of this, we still anticipate some missing values in the final datasets. Our basic tool to address this problem is multiple imputations. More specifically, if a variable is missing at V1, it will be imputed from the distribution of that variable of non-missing subjects. Due to the randomization at V1, non-missing subjects from both arms will be used for the distribution. For values missing at V3 (6 weeks after randomization), but non-missing at V2, the value collected at V2 will be carried forward in time via the LOCF (Last Observation Carried Forward) approach. For any instance where the participant remained in the trial, but did not provide data values at either post-randomization visit (V2 or V3), that case will be excluded from the analysis (modified ITT).

For some scenario, the missing values can be imputed by some reasonable assumptions. If a participant dropped out of the study prior to Visit 3 without providing Visit 2 data for the outcome, a 'worst-case-scenario' assumption will be made – assuming that the participant reverted back to exclusive smoking of cigarettes upon dropping out of the trial. Under this assumption, their Visit 2 baseline value will be carried forward to Visit 3. See the table below for a detailed outline of these methods:

V1	V2	V3	V` Baseline Result	V3 Endpoint Result	Mechanism of Missing		
+	+	+	Use directly Use directly		N/A		
+ + -			Lise directly	Impute V3 via LOCE from V2	Dropped out between V2 and V3		
	•	-			Missing V3 due to item non-response		
+	-	+	Use directly	Use directly	N/A		
-	+	+	Impute the V2 value from the overall sample distribution	Use directly	N/A		
			Use directly	Impute V3 via LOCF from V1	Dropped out between V1 and V2 Assume 'Worst-Case- Scenario'		
+	-	-	Excluded from Analysis (N	Dropped out between V2 and V3 Item Non-Response at V2			
			Excluded from Analysis (N	Completed the Switching Phase Missing V2 and V3 due to item non-response			
	Impute the V1 value		Impute the V1 value	Impute V2 via LOCE from V2	Dropped out between V2 and V3		
-	T	-	distribution		Missing V3 due to item non-response		
-	-	+	Impute the V1 value from the overall sample distribution	Use directly	N/A		
-	-	-	Excluded from Analysis (Modified ITT)				

Stratified Imputation Approach:

(+) = non-missing data(-) = missing data

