1.0 Objectives

1.1 Study Objectives

Our long term goal is to understand the likely health effects of cigarette smokers switching to a Standardized Research E-Cig (SREC) and to assess the role of nicotine delivery on switching, acceptability and markers of health outcomes. The specific objective of this proposal is to recruit a cohort of 240 current exclusive daily cigarette smokers and to measure a comprehensive battery of health markers at baseline and at 3 and 6 weeks after attempting to switch completely to SRECs containing either zero or 58 mg/ml nicotine in a randomized double-blind, placebo-controlled design with the following three specific aims:

- **1.1.1** Aim 1: To characterize the short-term effects of attempting to switch from traditional cigarette smoking to a Standardized Research E-Cig from baseline to 6 weeks using a comprehensive battery of measures (e.g. carcinogen biomarker (NNAL), pulmonary function testing, Holter EKG, exhaled CO, and cotinine, BP etc.).
 - **1.1.1.1** Our hypothesis is that attempting to switch to a SREC will result in a reduction in markers of harms to health, as compared with the baseline (exclusive cigarette smoking) measures.
- **1.1.2** Aim 2: To compare the effects of switching to a standardized research electronic cigarette (SREC) with pods containing 58 mg/ml nicotine liquid versus 0 mg/ml nicotine liquid on smoking behavior and changes in health markers at 6 weeks post-switching.
 - **1.1.2.1** Our hypothesis is that nicotine-containing SRECs will facilitate switching from smoking more efficiently than zero nicotine SRECs and will result in a significantly greater improvement in markers of health risk, but will conversely result in higher ratings of dependence on the SREC (as compared to the zero nicotine SREC) at 6 weeks post-switching (after controlling for baseline measures).
 - **1.1.2.2** We also hypothesize that the nicotine-containing SRECs, (as compared with the zero nicotine SRECs, after controlling for baseline) will result in a lower total score for the withdrawal items on the MNWS and lower mean scores on ratings of cigarette craving, during the first week of the trial.

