- **7.2.2.7** Following randomization, participants will receive the assigned study product (SREC with 0 mg/ml nicotine liquid or SREC with 58 mg/ml nicotine liquid; researcher and subject are blind to the nicotine dose), which will be pre-prepared by the unblinded research staff.
 - **7.2.2.7.1** Participants will be provided 2 rechargeable e-cig batteries, 1 wall adapter, 1 USB charger cord, a user manual, and a supply of pods, based on the participant's cigarette smoking (up to 22 pods). In a case where the participant will run out of pods, the participant will be able to come to the study to pick up an additional supply.
 - **7.2.2.7.2** Research staff will then explain how to use the device.
 - **7.2.2.7.3** Participants will be advised to cease all tobacco use and to start using their assigned e-cig product beginning the next morning.
 - **7.2.2.7.4** Participants will be provided with smoking cessation resources that are available in the community, and they will be encouraged to use them. In

addition, participants will be given the document from the Centers for Disease Control and Prevention titled, "A Report of the Surgeon General: How Tobacco Smoke Causes Disease."

- 7.2.2.7.5
- 7.2.2.7.6 Participants will be instructed to complete daily diaries related to their study product and cigarette use (E-cigarette Daily Diary includes place to record cigarette use as well). They will also be asked to return all used or unused e-cig pods at their next study visit.
- 7.2.2.7.7 Pulmonary Function Testing (PFTs) PFTs will be conducted as described in the Time and Events Table at Visits 1, 2, and 3. Any significant worsening (10% worsening or greater) in pulmonary function will be documented as an adverse event. All adverse events will be documented and reviewed by the Medical Monitor within 5 business days. In cases where the medical monitor suspects that a participant may be having a respiratory adverse event related to the study, a pulmonologist ([name]) will be consulted. The pulmonologist will make any needed medical recommendations and a determination regarding whether the participant is able to continue with the study.

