 - **7.2.2.7.7.1** When COVID protocols apply: The researcher will then leave the clinic space to complete the pulmonary function test, as the participant will need to remove their mask for this test. This will be facilitated by a two-way mirror and an intercom system. The researcher will remain outside of the clinic space for 15 minutes following the completion of this test and will use a timer to ensure that this time restriction is met.
- **7.2.2.8** Upon completion of the PFT test, participants will be given the opportunity to use the SREC device and ask the researcher any questions about its use prior to leaving the visit. The researcher will use the two-way mirror and intercom system to answer any questions.

(Part C): Visit Wrap-Up

- 7.2.2.9 Participants will then be provided with instructions to complete additional measures via a home computer/smart phone (see table of measures). A link to the surveys in REDCap will be sent to the participant's email address or phone. Participants will be instructed to complete all questionnaires within 24 hours. Participants unable to complete the questionnaires at home via a computer/smart phone will be called by the researchers to complete the questionnaires.
- **7.2.2.10** As the participant leaves the clinic space, participants will be provided with the Greenphire ClinCard.
 - **7.2.2.10.1** Once participants complete the additional questionnaires considered to be part of the visit (completed at home within 24 hours), they will be compensated for the visit. The funds will be automatically loaded onto the card.
 - **7.2.2.10.2** Those who do not complete the visit by completing the at-home questionnaires (which includes an option to opt-out of answering) will only be compensated for travel.

7.2.3 Switching Phase –Phone Contact #1 (Day 7 ± 7 days) and Phone Contact #2 (Day 14 ± 7 days) Note: While visit windows were extended to allow the participant flexibility, no visits (in person or phone), will occur on the same day.

During each phone contact, daily study product and cigarette use will be collected, adverse events or changes to concomitant medications will be documented, and participants will be asked to answer the measures indicated in the Time and Events Table. Participants will also be provided with advice/encouragement to remain abstinent from cigarettes. Participant's compensation for completing the phone call will be added to their gift card.

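### Section 8.3 starts the Aim 1 change at week 1, a phone contact after the switch, although Aim 1 and the section's own definition of baseline start at Visit 1 (week 0)

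*Combined protocol and SAP*

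**What the plan says.** Section 1.1.1 sets Aim 1 as the short-term effect of attempting to switch, "from baseline to 6 weeks using a comprehensive battery of measures". Its hypothesis (1.1.1.1) is a reduction in markers of harm "as compared with the baseline (exclusive cigarette smoking) measures". Section 1.1 states the measurement plan: "to measure a comprehensive battery of health markers at baseline and at 3 and 6 weeks after attempting to switch completely to SRECs".

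Section 8.3 opens with a general rule: "For the analysis, the baseline time will be Visit 1, prior to randomization". The Aim 1 paragraph then gives the estimate: "For each battery of measures, the mean change from week 1 to week 6 will be estimated". It adds a 95% confidence interval and a p-value for zero change, separately by arm, with false discovery control. A linear mixed model over Visits 1, 2 and 3 is described as an addition.

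On timing, Visit 1 is Day 0 and study week 0. At that visit participants are told to stop all tobacco and "start using their assigned e-cig product beginning the next morning" (7.2.2.7.3). Week 1 is Phone Contact #1, Day 7 with a window of 7 days either side (7.2.3).

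**The concern.** The aim and the rule that is meant to estimate it start at different times. The aim starts while participants smoke only cigarettes; the rule starts at a week that the schedule assigns to a telephone call after the switch.

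Two things follow if the rule is applied literally. For anything measured only in the clinic there is no starting value. For anything asked by telephone there is a starting value, but it is already a post-switch value, so the test of zero change addresses something other than the Aim 1 hypothesis. If the text stays ambiguous, the starting point for the diary and questionnaire measures may be settled only once the data are in hand.

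**Working it through.** **Step 1. The only power figure in the plan.** Section 8.2 claims at least 90% power for the between-arm NNAL comparison at week 6, with 84 per group, a difference of 35, SD 69 and 5% type 1 error (taken as two-sided). The standardized difference is 35 / (69 × √(2/84)) = 35 / 10.65 = 3.29. Power is Φ(3.29 − 1.96) = 90.8% (t-test version 90.5%). The 84 follows from 120 × 0.70. The figure reproduces, and it does not use a within-arm change. No power figure is given for Aim 1.

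**Step 2. What exists at each week.** From the Time and Events Table, read with the visit procedures in 7.2.2 to 7.2.6:

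| Measure | Week 0 (Visit 1) | Week 1 (Phone #1) | Week 3 (Visit 2) | Week 6 (Visit 3) |
|---|---|---|---|---|
| Urine NNAL, cotinine | yes | no | yes | yes |
| Exhaled CO | yes | no | yes | yes |
| Blood pressure | yes | no | yes | yes |
| Spirometry | yes | no | yes | yes |
| Holter EKG | yes | no | no | yes |
| Cigarettes per day (diary), Minnesota withdrawal scale, smoking urges | yes | yes | yes | yes |
| Product side effects | no | yes | yes | yes |
| E-cig dependence | no | no | yes | yes |

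All six measures named in Aim 1 have values at weeks 0 and 6, and none has one at week 1. A week 1 to week 6 change therefore does not exist for them.

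**Step 3. Where week 1 falls.** The window is Day 7 − 7 = Day 0 to Day 7 + 7 = Day 14. Since 7.2.3 rules out two contacts on one day, the call falls after Visit 1, on Day 1 to Day 14. Switching is due on the morning of Day 1. The literal starting point is thus post-switch and also varies between participants.

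**Step 4. What the literal contrast omits where it can be computed.** Write B, W1 and W6 for the values at weeks 0, 1 and 6.
- Aim 1 change: W6 − B.
- Change as written: W6 − W1.
- Difference between the two: W1 − B, the change from baseline smoking to the first week after the switch.

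If a fraction f of the total change has occurred by week 1, the written contrast keeps 1 − f of it. The documents give no f. Over an assumed range of 25% to 75%, it keeps 75% to 25%.

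The omission need not be a fall. Section 11.3 says that stopping cigarettes may bring on withdrawal symptoms. If withdrawal rose by d at week 1 and was back at B by week 6, the written contrast would be −d while the Aim 1 change would be zero.

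**Step 5. Scale of the baseline-anchored change.** Section 8.2 gives nicotine-arm NNAL means of 225 before and 80 after treatment (in the plan's units of ng/ml creatinine): 80 − 225 = −145, and 145 / 225 = 64%. Purely to show scale, if urine were collected at week 1 and 25% to 75% of that fall had occurred by then, the remaining fall would be 0.75 × 145 = 109 down to 0.25 × 145 = 36. No urine is collected at week 1, so this is not a prediction for NNAL.

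**The case against.** The strongest reply is that this is a labelling slip that the surrounding text resolves. Section 8.3 names Visit 1 as baseline; the mixed model in the same paragraph starts at Visit 1; the missing-data table pairs a V1 baseline with a V3 endpoint and has no week 1 column; and section 1.1 places the battery at baseline, 3 and 6 weeks. The document mislabels visits elsewhere too: section 8.2 puts the endpoint at Visit 4, and 7.4.5 puts randomization at Visit 2. An analyst who finds no week 1 urine would go back to Visit 1.

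Most of this stands, and a slip is the likeliest explanation. It does not remove the need for a correction. The other week numbers in the Aim 1 to 3 analyses follow the schedule (week 6 is Visit 3, week 10 is Phone Contact #5), and section 1.3 treats 1 week as a time point distinct from baseline for withdrawal and craving. The literal reading is therefore available for the measures that do have week 1 data. The missing-data text also speaks of a baseline value at Visit 2, so the section does not use one anchor throughout. The mixed model is an addition, with no week 0 to week 6 contrast specified from it.

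Three stronger readings are tempting, and the documents do not support them.
- A reader might infer that the NNAL or cardiopulmonary results would come out too small. They would not: with no week 1 value, the literal rule gives no number for them. Only the diary, withdrawal and urges measures could give a misleading one. Aim 1 does not name these, and withdrawal, craving and smoking behavior are placed mainly under Aim 2.
- A reader might infer that a first-week improvement in withdrawal or craving is being discarded. No passage predicts such a within-arm improvement, and 11.3 makes a rise in withdrawal plausible.
- A reader might infer a specific large loss for cigarettes per day. The documents give no expected course from which to calculate one.

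**Conclusion.** The Aim 1 estimate in section 8.3 is wrong as written. It contradicts the aim, the section's own baseline and the schedule. It cannot be computed for all six measures Aim 1 names. For cigarettes per day, withdrawal and urges it omits the change from week 0 to week 1, whose size and sign the documents do not give.

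The probable explanation, a slip for Visit 1 or week 0, is an inference from the surrounding text. The conclusion does not depend on it, because the same correction is needed either way.

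The reach is limited. The primary endpoint, the sample size, the power and the between-arm regressions under Aim 2, which already adjust for the baseline value, are unaffected.

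**What to change.** In the Aim 1 paragraph of section 8.3, define the change as running *from baseline (the Visit 1, week 0 assessment, before first SREC use) to week 6 (Visit 3)*, for every measure that has a Visit 1 value.

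Anchor on first SREC use rather than on randomization, because section 7.2.2 lists spirometry after randomization and dispensing but before participants try the device. The Visit 1 questionnaires done at home have a 24-hour window and may be completed after the device has been tried. The text should say that they still count as the week 0 value, and completion times should be kept so that late ones can be identified.

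For measures first collected after the switch (e-cig dependence, product side effects), report values over time rather than change from baseline. If the course after the switch is of interest for cigarettes per day, withdrawal and urges, report week 1 to week 6 separately as descriptive.

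The cost is a few lines of text. No new data, visits or participants are needed.
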